2.7.3 Handling of missing values/censoring/discontinuations

Subjects with missing PGIC score data at week 52 of treatment, and subjects that discontinue initially assigned treatment prior to week 52 will be imputed as non-responders (not achieving a net benefit).

For MMD values there will not be any missing data imputation.

2.7.4 Sensitivity / Supplementary analyses

Sensitivity analysis for secondary endpoint:

To assess impact of missing values on interpretation of results sensitivity analyses will be performed for secondary endpoint "Cumulative average change from baseline on the monthly migraine days during the treatment period week 4 to week 52 (Months 1-12)". Missing MMD data will be imputed using multiple imputation under MAR assumption. The multiple imputation model will be build based on similar subjects in the same treatment arm.

Supplementary analysis for secondary endpoint:

The supplementary analysis for secondary endpoint "Cumulative average change from baseline on the monthly migraine days during the treatment period week 4 to week 52

(Months 1-12)" is defined considering hypothetical strategy for subjects who are discontinuing early or switching initially assigned treatment.

This analysis will evaluate what if subject would have continued initially assigned treatment for 52 weeks

- if subject discontinues initially assigned treatment and does not switch to other SoC then missing data after discontinuation will be imputed using MAR. This is because we are considering what if subject would have continued initially assigned treatment.

- if subject switched to other SoC drug then for switched period until week 52 data will be considered as missing and such missing data will be imputed using MAR.

Points to note:

- The off-treatment MMD data and MMD data from switched drug cannot be used for analysis since it will not represent MMD values under initially assigned treatment.
- If MMD data is available say up to week 36 then data will be imputed from week 40 till week 52.

Table 2-5 Summary of secondary efficacy endpoints and analysis methods

Endpoint	Analysis	Imputation
Proportion of subjects completing the study at Month 12 on the initially assigned treatment	A Cochran-Mantel-Haenszel (CMH) test stratified by number of prior prophylactic migraine medication failures (1 vs. 2) will be used under a 2-sided significance level of 0.05.	No imputation.
Cumulative average change from baseline on the monthly migraine days during the treatment period week 4 to week 52 (Months 1-12)	The change from baseline will be analyzed using a linear mixed effects repeated measures model including treatment group, baseline value, stratification factor(s), scheduled visit, and the interaction of treatment group with scheduled visit.	No imputation.
	Sensitivity analysis: The change from baseline will be analyzed using a linear mixed effects repeated measures model including treatment group, baseline	Missing MMD data will be imputed using multiple imputation under MAR assumption. The multiple imputation model will be

	value, stratification factor(s), scheduled visit, and the interaction of treatment group with scheduled visit.	build based on similar subjects in the same treatment arm.
	Supplementary analysis: The change from baseline will be analyzed using a linear mixed effects repeated measures model including treatment group, baseline value, stratification factor(s), scheduled visit, and the interaction of treatment group with scheduled visit. This analysis will be performed considering hypothetical strategy for subjects who are discontinuing early or switching initially assigned treatment.	Intermittent missing MMD data will be imputed using multiple imputation under MAR assumption. To get imputed data for entire treatment period: 
- if subject discontinues initially assigned treatment and does not switch to other SoC then missing data after discontinuation will be imputed using MAR.- if subject switched to other SoC drug then for switched period until week 52 data will be considered as missing and such missing data will be imputed using MAR.
Proportion of responders as measured by PGIC at month 12 on the initially assigned treatment	A Cochran-Mantel-Haenszel (CMH) test stratified by number of prior prophylactic migraine medication failures (1 vs. 2) will be used under a 2-sided significance level of 0.05.	No imputation.

2.8 Safety analyses

For safety endpoints, all randomized subjects who received at least one dose of study treatment will be analyzed based on the actual treatment received (defined as the randomized treatment unless a subject has received the incorrect treatment during the treatment period).

Unless otherwise specified, all safety summaries and listings will be provided by initially assigned treatment group.

Missing data will not be imputed for safety endpoints.

2.8.1 Adverse events (AEs)

The Medical Dictionary for Regulatory Activities (MedDRA) version 20.0 or later will be used to code all adverse events (AE) to a system organ class (SOC) and a preferred term (PT). All adverse event tables will be summarized by treatment group.

For all AEs tables presented by SOC and PT (and grade), the SOCs will be presented in alphabetical order and PTs will be ordered within the SOC by decreasing order of frequency in the AMG334 treatment group. AE tables by preferred term only will be sorted in descending order of frequency in the AMG334 treatment group. A subject with multiple adverse events within a primary system organ class is only counted once towards the total of the primary system organ class.

Separate summaries by initially assigned treatment will be provided for study medication related adverse events, death, serious adverse events, adverse events leading to discontinuation and adverse events leading to dose adjustment.

All AEs, deaths, serious adverse events (SAE) and AEs leading to permanent study treatment discontinuation will be listed separately.

Summary of all AEs by SOC, PT and severity will also be provided by switched treatment. A separate listing of all AEs by initially assigned treatment and switched treatment will be provided.

Summary of treatment emergent AEs will be provided for COVID-19 and hypertension data by SMQ levels.

Summary of treatment emergent AEs will be provided for constipation by CMQ and corresponding preferred term.

Summary of exposure adjusted subject incidence rates for treatment emergent AEs and SAEs will be provided by primary system organ class and preferred terms.

2.8.1.1 Clinical trial safety disclosure (CTSD) reports

For clinicaltrials.gov and EuDRACT, two required tables on treatment emergent adverse events (TEAE) which are not SAEs with an incidence greater than a certain threshold based on the final database and on treatment emergent serious adverse events and SAEs suspected to be related to study drug will be provided by system organ class and PT on the safety set population.

If for a same subject, several consecutive AEs (irrespective of study drug causality, seriousness and severity) occurred with the same SOC and PT:

- a single occurrence will be counted if there is ≤ 1 day gap between the end date of the preceding AE and the start date of the consecutive AE
- more than one occurrence will be counted if there is > 1 day gap between the end date of the preceding AE and the start date of the consecutive AE

For occurrence, the presence of at least one SAE / SAE suspected to be related to study treatment / non SAE has to be checked in a block e.g., among AE's in a ≤ 1 day gap block, if at least one SAE is occurring, then one occurrence is calculated for that SAE.

The number of deaths resulting from SAEs suspected to be related to study treatment and SAEs irrespective of study treatment relationship will be provided by SOC and PT.

2.8.2 Deaths

Deaths will be listed by treatment including the start date of the study treatment, the last date on study treatment, the death date and the primary cause (and contributing cause if any) for death.

2.8.3 Laboratory data

Summary statistics will be presented for absolute as well as change from baseline of laboratory blood chemistry results by visit, initially assigned treatment and laboratory test category.

Subject incidence of liver enzyme abnormalities (including AST, ALT, Total Bilirubin (TBL) and Alkaline Phosphatase (ALP)) will also be summarized by treatment group.

Shift from baseline for some liver enzyme level categories (specified in the Tables, Figures and Listings (TFL) shells; for e.g. ALP<=1 x ULN) will also be provided by initially assigned treatment group.

Clinically notable laboratory values will be flagged and listed by treatment.

Parameters measured in the urine at screening including urine drug tests will be listed.

Table 2-6 Clinically Notable Laboratory Values

Notable Values			
Laboratory Variable	Gender (M/F/Both)	Standard Units	SI Units
LIVER FUNCTION AND RELATED VARIABLES			
SGOT (AST)	F	>93 U/L	>93 U/L
SGOT (AST)	M	>111 U/L	>111 U/L
SGPT (ALT)	F	>90 U/L	>90 U/L
SGPT (ALT)	M	>123 U/L	>123 U/L
Total bilirubin	Both	>3.6 mg/dL	>63 µmol/L
Alkaline Phosphatase	F	>832 U/L	>832 U/L
Alkaline Phosphatase	M	>1032 U/L	>1032 U/L
HEMATOLOGY VARIABLES			
Neutrophils	Both	<1.5x 10 ³ /uL	<1.5x10 ⁹ /L

Note: Only selected lab parameters which have potential to be sensitive to AMG334 exposure are listed.

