Subjects should be seen for all visits/assessments as outlined in the assessment schedule or as close to the designated day/time as possible. Missed or rescheduled visits should not lead to automatic discontinuation. Subjects who prematurely discontinue the study for any reason should be scheduled for a visit as soon as possible, at which time all of the assessments listed for the final visit will be performed. At this final visit, all dispensed investigational product should be reconciled, and the adverse event and concomitant medications recorded on the CRF.

Treatment discontinuation does not imply study discontinuation. Every effort should be attempted to ensure subjects complete the study visits event if treatment is discontinued.

If the **COVID-19 pandemic** limits or prevents on-site study visits, alternative methods of providing continuing care may be implemented. Phone calls, virtual contacts (e.g. teleconsult) or visits by site staff to the participant's home depending on local regulations and capabilities, can replace on-site study visits, for the duration of the pandemic until it is safe for the participant to visit the site again (see [Section 8.3](#) efficacy, [Section 8.4.1](#) Laboratory evaluations, [Section 8.4.3](#) Pregnancy, [Section 8.5.3](#) [REDACTED] and [Section 8.4](#) Safety monitoring.

Table 8-1 Assessment Schedule – Core Phase

Period	Screening			Open Label Randomized Treatment													
Visit Name	Screening	Baseline	Treatment	Week 4	Week 8	Week 12	Week 16	Week 20	Week 24	Week 28	Week 32	Week 36	Week 40	Week 44	Week 48	Week 52 / Early Exit ¹⁰	
Days	-42 to -28		-28 to -1		Day 1	28	56	84	112	140	168	196	224	252	280	308	364
Weeks	-6 to -4		-4 to -1		1	4	8	12	16	20	24	28	32	36	40	44	52
Informed consent	X																
Medical history/current medical conditions	X																
Demography	X																
Physical Examination ¹	X	X	X	X	X	X	X	X	X	X	X	X	X	X	X	X	X
Vital signs and body measurements	X	X	X	X	X	X	X	X	X	X	X	X	X	X	X	X	X
Electrocardiogram (ECG)	X									X							X
Pregnancy Test (serum) ²	X																X
Pregnancy test (urine) ²		X	X	X	X	X	X	X	X	X	X	X	X	X	X	X	X
Central blood chemistry - Erenumab	X		X							X							X
Central blood chemistry – SoC Oral Prophylactics ³	X		X	X ³	X ³	X ³	X ³	X ³	X	X ³							
Urine Drug Screen	X																
Columbia-Suicide Severity Rating Scale (C-SSRS) ⁴	X																
Randomization			X														
Study drug administration ⁵			X	X	X	X	X	X	X	X	X	X	X	X	X	X	X

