Contact IRT	X	X	X	X	X	X	X	X	X	X	X	X	X	X	X	X	
Clinical Outcome Assessment(s) ⁶		X	X	X	X	X	X	X	X	X	X	X	X	X	X	X	X
Patients' Global Impression of Change						X				X			X		X		X

Period	Screening			Open Label Randomized Treatment													
	Visit Name	Screening	Baseline	Treatment	Week 4	Week 8	Week 12	Week 16	Week 20	Week 24	Week 28	Week 32	Week 36	Week 40	Week 44	Week 48	Week 52 / Early Exit ¹⁰
Days	Days	-42 to -28	-28 to -1	Day 1	28	56	84	112	140	168	196	224	252	280	308	336	364
Weeks	Weeks	-6 to -4	-4 to -1	1	4	8	12	16	20	24	28	32	36	40	44	48	52
Adverse Events ⁹				X	X	X	X	X	X	X	X	X	X	X	X	X	X
Serious Adverse Events ⁹	X	X	X	X	X	X	X	X	X	X	X	X	X	X	X	X	X
Concomitant medications	X	X	X	X	X	X	X	X	X	X	X	X	X	X	X	X	X
Concomitant therapies	X	X	X	X	X	X	X	X	X	X	X	X	X	X	X	X	X
Core phase ¹⁰ completion																	X

^x Assessment to be recorded in the clinical database or received electronically from a vendor

¹ Full exam at Screening, Week 52. Height and weight will be measured at full exam. Short physical exam at all other visits.

² Results of pregnancy tests (serum or urine) will be captured as source and not in eCRF.

³ For subjects randomized to SoC oral prophylactics, central blood chemistry must be done at Screening, Treatment, Week 24, Week 52. All other visits, central blood chemistry to be done as needed for monitoring. Any additional safety measurements, if applicable, should be implemented as per label.

⁴ C-SSRS will be the electronic C-SSRS designed for computer administration (web or phone)

⁵ At every monthly study visit, the investigator should assess tolerability to randomized treatment (erenumab or SoC oral prophylactics) and determine if switching is appropriate. At Week 48, this will be the last dose of erenumab for subjects randomized to erenumab (monthly treatment). SoC oral prophylactics will continue to be dosed through month 12 as per label.

⁶ Patients will record migraine, headache, and headache medication information daily using the provided electronic diaries.

⁹ AE to be captured from Day 1 onward and SAE collection will be captured after informed consent is obtained.

¹⁰ Patients that complete Core Phase visits through Week 52 may be eligible to enter the Extension Phase. All patients will receive erenumab during the Extension Phase.

Table 8-2 Assessment Schedule – Extension Phase

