12.5.2 Safety endpoints

For all safety analyses, the safety set will be used. All listings and tables will be presented by treatment group.

Safety summaries (tables, figures) include only data from the on-treatment period with the exception of baseline data which will also be summarized where appropriate (e.g. change from baseline summaries). In addition, a separate summary for death including on treatment and post treatment deaths will be provided. In particular, summary tables for adverse events (AEs) will summarize only on-treatment events, with a start date during the on-treatment period (*treatment-emergent* AEs).

The on-treatment period lasts from the date of first administration of study treatment to 112 days after the date of the last actual administration of any study treatment.

Adverse events

All information obtained on adverse events will be displayed by treatment group and subject.

The number (and percentage) of subjects with treatment-emergent adverse events (events started after the first dose of study medication) will be summarized in the following ways:

- by treatment, primary system organ class and preferred term.
- by treatment, primary system organ class, preferred term and maximum severity.
- by treatment, Standardized MedDRA Query (SMQ) and preferred term

Separate summaries will be provided for study medication related adverse events, death, serious adverse events, other significant adverse events leading to discontinuation and adverse events leading to dose adjustment.

A subject with multiple adverse events within a primary system organ class is only counted once towards the total of the primary system organ class.

Vital signs

All vital signs data will be listed by treatment group, subject, and visit and if ranges are available, abnormalities will be flagged. Summary statistics will be provided by treatment.

12-lead ECG

All ECG data will be listed by treatment group, subject and visit/time, abnormalities will be flagged. Summary statistics will be provided by treatment.

Clinical laboratory evaluations

All laboratory data will be listed by treatment group, subject, and visit and if normal ranges are available abnormalities will be flagged. Summary statistics will be provided by treatment. Shift tables using the low/normal/high/ (low and high) classification will be used to compare baseline to the worst on-treatment value.

[REDACTED]

[REDACTED]

[REDACTED]

[REDACTED]

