2.14 Interim analysis

Not Applicable.

3 Sample size calculation

The sample size calculation is based on the primary variable, rate of net benefit. The details of hypothesis testing are described in [section 2.5.2](#).

A 2-sided test with significance level 0.05, and a 2:1 randomization ratio are considered. A sample size of 591 (394 erenumab arm; 197 control arm) is required to achieve 90% power to reject the odds ratio of 1 set by the null hypothesis when the odds ratio is actually 2, and success rate in control arm is 0.18.

An odds ratio of 2 and control rate of 0.18 is based on more conservative assumptions for rate of net benefit than observed previously (for erenumab in studies NCT02456740, NCT01952574, and oral cycling in Hepp et al 2017, Shei et al 2015), resulting in a rate difference of 12%. Sample size calculations were done using PASS 11 and Cochran-Mantel-Haenszel test was used.

4 Change to protocol specified analyses

Not applicable.

5 Appendix

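### Liver-enzyme incidence and worst-value shifts are not limited to shared visits, although only the oral arm may have as-needed chemistry at up to 11 further visits

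*SAP*

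**What the plan says.** Protocol Table 8-1 has a separate chemistry row for each arm. The row "Central blood chemistry - Erenumab" carries four marks: Screening, Treatment (Day 1), one mid-study visit and Week 52/Early Exit. For the oral arm, footnote 3 fixes the same number of mandatory draws: "For subjects randomized to SoC oral prophylactics, central blood chemistry must be done at Screening, Treatment, Week 24, Week 52". It then adds: "All other visits, central blood chemistry to be done as needed for monitoring". There is no matching provision in the erenumab row.

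Two outputs use these data:

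- SAP 2.8.3: "Subject incidence of liver enzyme abnormalities (including AST, ALT, Total Bilirubin (TBL) and Alkaline Phosphatase (ALP)) will also be summarized by treatment group". The same section plans "Shift from baseline for some liver enzyme level categories" by initially assigned arm, with the categories left to the table shells. It does not say which post-baseline value is used.
- Protocol 12.5.2: "Shift tables using the low/normal/high/ (low and high) classification will be used to compare baseline to the worst on-treatment value". SAP Section 4, headed "Change to protocol specified analyses", is marked not applicable, so the worst-value rule stands.

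SAP 2.1.1.6 assigns laboratory values to windows for all 13 post-baseline visits and keeps one value per window. SAP 2.8.1 plans exposure-adjusted rates for adverse events and serious adverse events only.

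**The concern.** The share of subjects with any abnormal value, and the worst value per subject, both depend on how often a subject is sampled. For a given length of follow-up, an extra draw can only leave these measures unchanged or raise them. If one arm may be sampled at visits where the other is not, the table mixes drug effect with sampling intensity.

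Nothing in the plan removes this. The window rule limits values within a window, not the number of windows that count. Because every 4-weekly visit has a window, an as-needed oral draw becomes an ordinary analysis-visit value. As-needed draws may also be prompted by symptoms or by the drug in use, which adds selection.

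Protocol 4.1 presents the trial as a source of head-to-head safety data. In an open-label study, a hepatic table that could favour erenumab because of draw counts invites misreading.

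**Working it through.** The documents give no laboratory incidence and no expected number of as-needed draws, so there is no plan figure to reproduce. Draw counts come from the documents. Per-draw risk, as-needed uptake and within-subject correlation are assumptions, shown over ranges.

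**Step 1: count the draws.** Visits every 4 weeks from Week 4 to Week 52 give 52/4 = 13 post-baseline visits.

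- Erenumab: 2 scheduled.
- Oral: 2 mandatory (Weeks 24 and 52), plus as-needed draws at up to 13 − 2 = 11 visits (five in Weeks 4–20, six in Weeks 28–48).

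**Step 2: equal true risk, independent draws.** Let p be the chance that a draw is abnormal, the same in both arms, and q the share of as-needed visits actually sampled.

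- Erenumab: P(any abnormal) = 1 − (1 − p)²
- Oral: P(any abnormal) = 1 − (1 − p)²(1 − qp)¹¹

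At p = 1%, erenumab is 1 − 0.99² = 1.99%. For the oral arm:

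| q | Oral, any abnormal | Ratio oral:erenumab |
|---|---|---|
| 0 | 1.99% | 1.00 |
| 10% | 3.06% | 1.54 |
| 25% | 4.65% | 2.34 |
| 50% | 7.25% | 3.64 |
| 100% (13 draws) | 12.25% | 6.15 |

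The ratio depends little on p. At q = 10% it runs from 1.55 (p = 0.2%) to 1.50 (p = 5%). At q = 100% it runs from 6.43 to 4.99.

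**Step 3: correlation between a subject's draws.** Use a beta-binomial with mean m = 0.01 and correlation ρ: a = m(1 − ρ)/ρ, b = (1 − m)(1 − ρ)/ρ, and P(none in k draws) = Γ(b + k)Γ(a + b)/[Γ(b)Γ(a + b + k)]. For 13 against 2 draws:

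| ρ | Oral (13 draws) | Erenumab (2 draws) | Ratio |
|---|---|---|---|
| 0.1 | 8.0% | 1.9% | 4.2 |
| 0.3 | 4.7% | 1.7% | 2.8 |
| 0.5 | 3.1% | 1.5% | 2.1 |

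**Step 4: the effect that works the other way.** Suppose laboratory data stop when initially assigned treatment stops.

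- Erenumab: with retention of about 90% at 6 months (protocol 4.5) and 77.5% at one year (midpoint of 75–80%, protocol 1.1), expected mandatory draws are 0.90 + 0.775 = 1.675.
- Oral: protocol 1.1 cites 13–16% one-year persistence, from chronic-migraine claims data. Assuming exponential decline, S(24) = S(52)^(24/52), expected mandatory draws are 0.39 + 0.13 = 0.52 to 0.43 + 0.16 = 0.59.
- Summing the same curve over the 11 as-needed visits gives 4.60 to 4.96 available. Draws per subject are then equal when q = (1.675 − 0.52)/4.60 = 25% to (1.675 − 0.59)/4.96 = 22%.
- If oral persistence were 50%, the break-even would be (1.675 − 1.23)/7.90, about 6%.

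**Step 5: shared visits only.** Two draws against two give a ratio of 1.00 at any p, with equal risk and follow-up.

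The table layout was damaged in extraction, so the column of the erenumab mid-study mark should be confirmed as Week 24. The count of two does not depend on it.

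**The case against.** The strongest reply is that the compulsory schedule is the same, two draws against two, and as-needed sampling may be rare. That is correct: 13 is a ceiling and the effect could be close to zero. A reader might take a two-and-a-half- to six-fold distortion from the arithmetic. That would need 5 to 13 independent draws per oral subject, and the documents support neither the count nor the independence.

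A reader might also infer that this is the trial's only head-to-head hepatic comparison. It is not. SAP 2.8.3 also summarises chemistry by visit and arm, which at the shared visits is a like-for-like comparison, and adverse events are tabulated by arm. Those summaries do not give incidence or worst-value shift, so they cover the gap only in part.

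Nor is a bias in favour of erenumab established. Liver follow-up in protocol 10.2.1 and 16.2 can generate repeat tests in either arm, so two is not a hard cap on erenumab, and early oral discontinuation pulls the other way (Step 4). The protocol's on-treatment period extends 112 days past the last dose of any study treatment, which weakens that offset. SAP 2.8.3 does not say which period applies. Two opposing effects of unknown size do not make the table unbiased.

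Subject incidence is not defined as abnormal at any visit. The SAP specifies by visit for ECG and any post-baseline visit for vital signs, but neither for liver enzymes, and the shells are not available. If incidence were shown by visit, that table would largely escape, but the protocol's worst-value shift would not. It would also go too far to say that the extra chemistry is label-driven: footnote 3 calls it as needed and mentions the label for additional safety measurements.

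Finally, replacing the all-draw tables with Weeks 24 and 52 alone could lose early-exit and as-needed abnormal values. That objection stands, and it shapes the fix.

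**Conclusion.** The concern holds as a possible, unquantified distortion of two descriptive outputs. With equal risk and equal follow-up, the plan as written can show more liver-enzyme abnormality on oral drugs because those subjects may be drawn more often. Under an equal 1% per-draw risk and independent draws, the ratio is 1.0 with no as-needed sampling, about 1.5 at 10% uptake, 2.3 at 25%, and at most about 6 at all 13 visits. Correlation lowers it, to 2.1 even at the ceiling when ρ = 0.5. If data are cut at the end of initially assigned treatment, early oral discontinuation could cancel or reverse it. No between-arm laboratory test is planned, so no formal inference is affected. What is at stake is how the safety tables are read, and the remedy is cheap enough to be worth making.

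**What to change.** In SAP 2.8.3:

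- Make the between-arm liver-enzyme incidence and worst-value shift tables use the visits scheduled in both arms: Week 24 and Week 52/Early Exit. Count an Early Exit draw as such whichever study-day window it falls in, so that subjects who leave early are not dropped.
- Keep the all-draw incidence and shift tables beside these, with the number of chemistry draws per subject by arm.
- State whether incidence means any visit or each visit, and which treatment period supplies the values.
- Keep every value in the listings and in liver-event follow-up, so that no case is hidden.

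The cost is SAP wording and one or two extra tables, with no new samples. The common-visit table will hold fewer events, and differential retention will still affect who is sampled, so show the number of subjects sampled at each shared visit.

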2.8.4 Other safety data

2.8.4.1 ECG and cardiac imaging data

The ECG measurements from this clinical study will be performed as per standard of care for routine safety monitoring, rather than for purposes of assessment of potential QTc effect. Subject incidence of abnormal ECG diagnosis (see [Table 2-7](#)) will be summarized by treatment group and by visit for initially assigned treatment.

ECG measurements with abnormalities will be listed by treatment.

However, since these evaluations may not necessarily be performed under the rigorous conditions expected to lead to meaningful evaluation of QTc data, these data are not expected to be useful for meta-analysis with data from other trials.

Table 2-7 ECG Abnormality Ranges

ECG Parameter	Abnormality Flags	
	Absolute	Relative*
RR Interval	Low: < 600 msec ; High: > 1200 msec	Low: $\leq -20\%$; High: $\geq 20\%$
PR interval	Low: < 120 msec ; High: > 200 msec	Low: $\leq -20\%$; High: $\geq 20\%$
QRS Interval	Low: < 60 msec ; High: > 109 msec	Low: $\leq -20\%$; High: $\geq 20\%$
QT Interval	Low: < 320 msec ; High: > 450 msec	Low: $\leq -20\%$; High: $\geq 20\%$
QTcB Interval (Bazett's correction)	Low: < 320 msec ; High: > 450 msec	Low: $\leq -20\%$; High: $\geq 20\%$
QTcF Interval (Fridericia's correction)	Low: < 320 msec ; High: > 450 msec	Low: $\leq -20\%$; High: $\geq 20\%$

*Relative change from previous measurement in percent (%)

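### The SAP narrows the protocol's laboratory shift tables and normal-range flagging to liver tests and a short notable-values list, and omits ECG interval statistics, while declaring no change from the protocol

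*SAP*

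**What the plan says.** Protocol 12.5.2 makes these commitments for laboratory data and ECGs:

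- Laboratory listing: "All laboratory data will be listed by treatment group, subject, and visit and if normal ranges are available abnormalities will be flagged".
- Laboratory shifts: "Shift tables using the low/normal/high/ (low and high) classification will be used to compare baseline to the worst on-treatment value". The sentence is not limited to liver tests.
- ECG: "All ECG data will be listed by treatment group, subject and visit/time, abnormalities will be flagged. Summary statistics will be provided by treatment".

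SAP 2.8.3 keeps one general laboratory output: "Summary statistics will be presented for absolute as well as change from baseline of laboratory blood chemistry results by visit". Its other laboratory outputs are narrower. Incidence of abnormality is named for AST, ALT, total bilirubin and alkaline phosphatase. Shifts are described as "Shift from baseline for some liver enzyme level categories", with the categories left to the table shells. Flagging applies to clinically notable values, which Table 2-6 defines for those four liver tests and neutrophils. A note under that table says: "Only selected lab parameters which have potential to be sensitive to AMG334 exposure are listed".

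SAP 2.8.4.1 plans the incidence of ECG abnormality by arm and visit, using the ranges in Table 2-7, and then: "ECG measurements with abnormalities will be listed by treatment". It names no summary statistics for the ECG intervals.

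SAP section 4, headed "Change to protocol specified analyses", is marked as not applicable. The SAP's document history logs neither reduction.

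**The concern.** Protocol Table 4-1 presents the trial as a head-to-head source of efficacy and safety data against oral prophylactics. A shift table by arm is the usual way to show how many subjects left the normal range during treatment, and in which direction. If it exists only for liver tests, the report may contain no count of out-of-range values for any other chemistry analyte, in either arm.

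By-visit summaries do not replace it. They describe the distribution at each visit, and they neither count subjects nor pick out each subject's worst value. The protocol does expect some extra laboratory monitoring: footnote 3 of Table 8-1 allows as-needed chemistry at other visits for the oral arm.

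There is also a point of traceability. A programmer working from the SAP would produce less than the protocol promises, and a reader of section 4 would be told that nothing had changed.

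**Working it through.** The plan attaches no figure to these tables, so there is nothing to reproduce. The check is a comparison of the two texts.

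| Item | Protocol 12.5.2 | SAP |
|---|---|---|
| Laboratory summary statistics | By treatment | 2.8.3: value and change, by visit and arm (kept) |
| Laboratory flagging | All data, where normal ranges exist | 2.8.3: Table 2-6 notable values only |
| Shift table | Low/normal/high/(low and high), baseline to worst on-treatment value, no restriction | 2.8.3: some liver categories, detail in shells |
| ECG listing | All data, abnormalities flagged | 2.8.4.1: abnormal measurements only |
| ECG summary | Summary statistics by treatment | 2.8.4.1: incidence of abnormality only |
| Declared change | n/a | Section 4: none |

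Three further places bear on the reading.

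1. SAP 2.1 defines descriptive statistics for quantitative data as mean, SD, median, minimum and maximum. Non-liver chemistry therefore gets these five by visit, not means alone.
2. SAP 5.3, on laboratory derivations, is empty (NA), so no normal-range classification is defined elsewhere in the SAP.
3. SAP 2.8.4.2 does state change-from-baseline statistics for vital signs. The SAP says so where it plans them, so their absence for ECG reads as an omission.

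**Illustration with assumed rates.** No document gives rates of laboratory abnormality. Take the planned arms, 394 erenumab and 197 oral, and suppose one analyte moves by 2 SD of change in the affected subjects and by nothing on average in the rest.

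- SE of the difference in mean change = sqrt(1/394 + 1/197) = 0.087 SD.
- Difference in mean change = (oral rate − erenumab rate) × 2 SD, and z = difference / 0.087.

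| Affected, oral | Affected, erenumab | Difference in means | z | Fisher exact p on the counts |
|---|---|---|---|---|
| 10/197 (5.1%) | 4/394 (1.0%) | 0.081 SD | 0.93 | 0.0037 |
| 6/197 (3.0%) | 4/394 (1.0%) | 0.041 SD | 0.47 | 0.09 |
| 10/197 (5.1%) | 10/394 (2.5%) | 0.051 SD | 0.58 | 0.15 |

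With a 3 SD move, the first row gives 0.122 / 0.087, or z = 1.40. In each row the count separates the arms more clearly than the mean does, but how clearly depends wholly on the assumed rates. Neither document plans a test on shift tables; the p-values only compare how visible the difference is.

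**Sampling opportunity.** Table 8-1 and its footnote 3 schedule post-baseline chemistry at Week 24 and Week 52 in both arms, which is 2 samples. In the oral arm, as-needed sampling can add any other visit, up to 52/4 = 13 four-weekly visits. If each sample is out of range with probability q, independently, a subject with k samples has probability 1 − (1 − q)^k of at least one abnormal value. This rises with k even when q is the same in both arms, so a worst-value table on its own could tilt against the oral arm.

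**The case against.** The strongest reply is that this is a small mismatch of text. SAP section 1 says the data will be analysed according to protocol section 12, which still contains the full listing and flagging. The table shells are not among the documents and may hold more, and protocol 12.5.2 has redacted lines after the laboratory paragraph. Clinically significant, symptomatic or treated laboratory values become adverse events in both arms under protocol 10.1.1. For ECG, the protocol does not say that its summary statistics must be continuous, and the SAP explains that the tracings serve routine monitoring.

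Part of this stands. The ECG gap is a narrowing, because abnormality incidence for six parameters remains. But a general pointer to the protocol does not repair a SAP that goes on to specify less, and 2.8.3 cites the shells only for the liver categories.

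Four stronger readings are tempting and are not supported.

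- A reader might infer that the shift categories were chosen for sensitivity to erenumab. That note belongs to Table 2-6, the notable-values list. The SAP gives no reason for the choice of shift categories.
- A reader might infer that non-liver abnormalities are never classified, or surface only as adverse events. Neutrophils are in Table 2-6, and by-visit minimum and maximum show extremes.
- A reader might infer a bias in one direction. The reduced tables apply equally to both arms.
- A reader might name particular comparator drugs whose effects would be hidden. The drug classes in exclusion criterion 4 define prior treatment failure and are not a list of the comparators used. The documents also do not list the central chemistry analytes.

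**Conclusion.** The reduction is real and undeclared. Against protocol 12.5.2, the SAP specifies no low/normal/high classification or shift table for non-liver chemistry in either arm, flags only Table 2-6 values, lists only abnormal ECGs and names no ECG interval statistics. Section 4 reports no change.

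The size is modest. It concerns descriptive safety tables and does not touch the primary or secondary efficacy analyses. How much information would be lost cannot be derived from the documents; the illustration above rests on assumed rates and shows only that counts can reveal what means do not. The conclusion assumes that the unseen table shells do not restore the missing tables and that the redacted protocol lines do not withdraw them. Because the tables are cheap and the protocol already promises them, the two texts should be reconciled.

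**What to change.** - **SAP 2.8.3:** restore the protocol's shift table, baseline to worst on-treatment value in the low/normal/high/(low and high) classes, for every central chemistry analyte in both arms. Restore flagging against normal ranges in a listing of all laboratory data. Keep the liver categories and Table 2-6 as additions.
- **Unequal sampling:** show the same shift table restricted to the chemistry visits scheduled in both arms (Week 24 and Week 52), so that extra as-needed oral-arm samples do not drive a difference.
- **SAP 2.8.4.1:** add summary statistics of value and change from baseline for the ECG parameters by arm, and list all ECG data with abnormalities flagged.
- **SAP section 4:** if any of these reductions is intended, declare it there with the reason.

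The cost is SAP wording and a few more standard descriptive tables from data already collected. No new assessments are needed.
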